First dose of nivolumab will be administered on Cycle 1 Day 8, which is only 2 weeks away from Cycle 2 Day 1. For safety reasons, subjects may be dosed no less than 12 days between doses. For all other cycles, treatment is to occur within 3 days of the scheduled dosing date. Dose given after the 3 day window is considered a dose delay. Treatment may be delayed for up to a maximum of 6 weeks from the previous dose. Refer to [Section 4.5.4](#) for further details.

Subjects will be monitored continuously for AEs while on study. Treatment modifications (eg, dose delay, interruption or discontinuation) will be based on specific laboratory and AE criteria (further details described in [Section 4.5.3](#) and [Section 4.5.4](#)).

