4.5.1 Dose Evaluation Phase: (Cohort A)

The Dose Evaluation Phase (Cohort A) will include a dose limiting toxicity (DLT) evaluation for the dose level of brentuximab vedotin 1.8 mg/kg intravenously in combination with nivolumab 240 mg flat dose intravenously in a q 3 week cycle. In cycle 1, brentuximab vedotin 1.8 mg/kg will be administered on day 1 where as nivolumab 240 mg flat dose will be administered on day 8. Subsequent to cycle 1, both drugs will be administered on the first day of the new cycle. Brentuximab vedotin will be administered first as a 30-minute infusion followed by a minimum 30-minute rest. Nivolumab will be then be administered as a 30-minute infusion.

The DLT evaluation will be conducted in the first 6 treated subjects (all comers). Decisions to enroll up to 6 additional subjects onto the same dose of brentuximab vedotin 1.8 mg/kg in combination with nivolumab 240 mg flat dose intravenously every 3 weeks or at a reduced dose of brentuximab vedotin at 1.2 mg/kg will be based on the safety data reviewed throughout the DLT evaluation period. The DLT evaluation period consists of the first dose of study drug through the first 6 weeks of treatment.

If any of the first 6 treated subjects discontinue treatment for reasons other than a DLT, prior to completing the DLT evaluation period, then they will be replaced. These subjects will be monitored for DLT throughout the DLT evaluation period (DLT definition is provided further below in this section). After 6 DLT-evaluable subjects have been followed through the end of the DLT evaluation period, or at the point that 2 or more subjects experience a DLT, whichever comes first, the study team will review the available data. The BMS study team along with Seattle

Genetics study team and the investigators participating in the trial, will review all of the available safety data and provide any of the following recommendations that may include, but are not limited to:

1. One or none (≤ 1) of the 6 subjects experience a DLT, the expansion cohort will begin with brentuximab vedotin 1.8 mg/kg Cycle 1 Day 1 and nivolumab 240 mg flat dose on Cycle 1 Day 8. Subsequent to cycle 1, both drugs will be administered on the first day of the new cycle. Brentuximab vedotin will be administered first as a 30-minute infusion followed by a minimum 30 minute rest. Nivolumab will be then be administered as a 30 min infusion.

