2. If two or more (≥ 2) of the 6 subjects are determined to have had a DLT based on the protocol definition, the following options will be considered
 - a. To repeat Cohort A of the study and treat up to 6 additional subjects at the same drug doses and schedule previously tested
 - b. To repeat Cohort A of the study and treat up to 6 additional subjects at a reduced dose of brentuximab vedotin 1.2 mg/kg;
 - c. Administration of the combination treatment on Day 1 of every cycle, including cycle 1
 - d. To close the study to additional enrollment.

NOTE: Doses may not be increased to above 1.8 mg/kg brentuximab vedotin or nivolumab 240 mg flat dose

On review of all available data, the study team may determine that the classification of DLT was not appropriate for one or more of the subjects, in which case enrollment may resume if the target of 6 DLT-evaluable subjects has not yet been reached. However, if 2 or more subjects were determined to have experienced DLTs, then expansion will not occur as the next step. Based on the study team's recommendations, up to 6 additional subjects may be enrolled in Cohort A at the same drug doses and schedule or at a modified treatment (described above in this section). These additional subjects will then be assessed for DLT in the same manner described above to determine if it is appropriate to move to the Expansion Phase (Cohort B). If it is determined by the study team that due to safety concerns no additional dose levels or schedules should be enrolled, then the study will be closed to enrollment.

Dose Limiting Toxicity

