The incidence of dose limiting toxicities assessed in the first 6 DLT-evaluable subjects beginning Cycle 1 Day 1 through the first 6 weeks of treatment will determine whether the combination, nivolumab with brentuximab vedotin is tolerable. A subject will be considered evaluable for DLT if they have received at least one dose of either drug in the first 6 weeks of treatment. However, if the subject discontinues treatment for reasons other than a DLT prior to completing the DLT evaluation period, then they are **not** considered DLT evaluable and will be replaced. DLT should not be AEs considered by the investigator to be disease related. For the purpose of this study, DLTs are defined as any study drug-related toxicity (brentuximab vedotin or nivolumab) that requires either a dose reduction or delay of more than 7 days of either study drug in Cycle 2 or delays the Cycle 3 Day 1 administration of combined treatment by more than 7 days. The DLT evaluation period consists of the first dose of study drug through the first 6 weeks of treatment. The IBs for

brentuximab vedotin and nivolumab individually describe adverse events commonly observed relative to either agent (ie, neutropenia or peripheral neuropathy with brentuximab vedotin; immune-mediated adverse events with nivolumab), as well as less common serious findings. However, the final decision regarding causality is at the discretion of the Investigator.

There is no planned interim analysis (IA). However, all available efficacy and safety data will be used to select the recommended dose that will be further evaluated in the Expansion Phase (Cohort B).

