4.5.4.2 Criteria to Resume Nivolumab Dosing

Subjects may resume treatment with nivolumab when the drug-related AE(s) resolve to Grade ≤ 1 or baseline value, with the following exceptions:

- Subjects may resume treatment in the presence of Grade 2 fatigue
- Subjects who have not experienced a Grade 3 drug-related skin AE may resume treatment in the presence of Grade 2 skin toxicity
- Subjects with baseline AST/ALT or total bilirubin in the Grade 1 toxicity range who require dose delays for reasons other than a 2-grade shift in AST/ALT or total bilirubin may resume treatment in the presence of Grade 2 AST/ALT OR total bilirubin
- Subjects with combined Grade 2 AST/ALT AND total bilirubin values meeting discontinuation parameters ([Section 4.5.5](#)) should have treatment permanently discontinued
- Drug-related pulmonary toxicity, diarrhea, or colitis must have resolved to baseline before treatment is resumed
- Drug-related endocrinopathies adequately controlled with only physiologic hormone replacement may resume treatment.

If nivolumab treatment is delayed for any reason, brentuximab vedotin must also be delayed until the subject has appropriately recovered and is able to resume the combination treatment on the first day of the subsequent cycle. Brentuximab vedotin should only be given alone in case a decision has been made to permanently discontinue nivolumab.

If treatment is delayed > 6 weeks, the subject must be permanently discontinued from study therapy, except as specified in [Section 4.5.5](#).

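### The protocol's DLT definition does not name drug-related discontinuation or death, and the SAP adds only discontinuation, so the decision count and the reported count can differ

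*Protocol*

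**What the plan says.** **Definition.** Under Protocol Section 4.5.1 a DLT is drug-related toxicity that "requires either a dose reduction or delay of more than 7 days of either study drug in Cycle 2", or that "delays the Cycle 3 Day 1 administration of combined treatment by more than 7 days". The window is the first 6 weeks of treatment.

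**Evaluability.** One dose of either drug makes a subject evaluable. However, "if the subject discontinues treatment for reasons other than a DLT prior to completing the DLT evaluation period", that subject is not evaluable and is replaced.

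**Decision rule.** With at most one DLT in six, expansion begins. The alternative options apply when two or more "are determined to have had a DLT based on the protocol definition", and the section adds: "if 2 or more subjects were determined to have experienced DLTs, then expansion will not occur as the next step".

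**Stops inside the window.** Sections 4.5.3 and 4.5.5 require a Cohort A subject who meets discontinuation criteria during the DLT period to stop both drugs. Neither section calls this a DLT. Section 4.5.5 requires nivolumab to be stopped for Grade 3 drug-related pneumonitis of any duration.

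**SAP.** Section 4.1 lists DLT among the primary safety endpoints. Section 7.6.1 restates the protocol definition. Its next paragraph classifies Cohort A subjects as having a DLT if a related adverse event requires discontinuation, reduction or delay. Death is not mentioned. The table covers all treated Cohort A subjects.

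**The concern.** The definition lists actions on dosing, and the two most severe outcomes are not among them. Read literally, a Grade 2 neuropathy that leads to a reduction to 1.2 mg/kg in Cycle 2 counts (Protocol Table 4.5.3-1). A Grade 3 pneumonitis that ends treatment in Cycle 1 does not, and that subject is replaced.

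The protocol's own background shows that such an event can fall early. Section 1.4.3 reports a fatal pneumonitis with onset 10 days after a single nivolumab dose. In this schedule nivolumab is first given on Day 8, so the same timing gives Day 8 + 10 = Day 18. That is before Cycle 2 Day 1 (Day 22), when no Cycle 2 dose has yet come due to be reduced or delayed.

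Two things are at stake. The first is the count that gates expansion. The second is a primary safety endpoint for which the protocol and the SAP give different counting rules, so a reader of the report cannot tell which rule produced the decision.

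**Working it through.** **1. The counting rules side by side**

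| Drug-related event in the 6-week window | Protocol 4.5.1 | SAP 7.6.1, first definition | SAP 7.6.1, categorization paragraph |
|---|---|---|---|
| Dose reduction or delay over 7 days in Cycle 2 | DLT | DLT | DLT |
| Cycle 3 Day 1 over 7 days late | DLT | DLT | DLT |
| Permanent discontinuation | not named; replaced on a literal reading | not named | DLT (could be read as Cycle 2 only) |
| Death | not named | not named | not named |

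**2. Is a stop already a delay?** The protocol uses the two words for different actions. Section 4.5 says: "Treatment modifications (eg, dose delay, interruption or discontinuation) will be based on specific laboratory and AE criteria". Section 4.5.4.2 makes one the consequence of the other: "If treatment is delayed > 6 weeks, the subject must be permanently discontinued from study therapy". The SAP also found it necessary to add discontinuation as a separate term. So the text does not settle that a permanent stop counts as a delay.

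**3. Reproduce the plan's figures.** Protocol Section 8.1 gives one-sided 80% exact upper limits of 42% (fewer than 1/3 of 6, so at most 1) and 41.2% (fewer than 1/3 of 12, so at most 3). The Clopper-Pearson upper limit for x events in n is the 0.80 quantile of Beta(x + 1, n − x).

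- 1/6: Beta(2, 5) gives 42.24%. This agrees with the plan.
- 3/12: Beta(4, 9) gives 41.24%. This agrees with the plan.

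**4. Add one uncounted event**

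| Counted | Upper limit | With the event counted | Upper limit | Decision |
|---|---|---|---|---|
| 0/6 | 23.5% | 1/6 | 42.2% | go in both cases |
| 1/6 | 42.2% | 2/6 | 58.5% | go becomes no expansion as the next step |
| 1/6 | 42.2% | 2/7 (replacement kept in the denominator) | 51.7% | same change |

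The 2/6 row assumes that the named DLT was in one of the original subjects and not in the replacement. At a counted 2 or more, expansion is already blocked. So a single uncounted event changes the decision only when the counted number is exactly 1. Two uncounted events with a counted 0 would also reach 2, which is a more remote case.

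**The case against.** The strongest reply is that the third limb already covers these cases. A Cohort A subject who stops for toxicity must stop both drugs, so combined treatment cannot be given on Cycle 3 Day 1 within 7 days of its due date. A drug-related death has the same effect. The replacement clause also presupposes that some subjects stop because of a DLT. This reading is plausible and may be what was intended. It is not what the text says, and it leaves both the mismatch with the SAP and the silence on death.

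Several other points stand and limit the concern:

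- The sponsor teams and investigators "review all of the available safety data and provide any of the following recommendations that may include, but are not limited to". A toxic death would not go unseen merely because it was not labelled a DLT.
- Deaths and discontinuations are primary safety endpoints in their own right.
- SAP Sections 7.3.1, 7.4.2.3 and 7.6.1 already plan listings or summaries of last dose dates, off-study reasons, reasons for discontinuation (including single-drug stops) and details of DLT subjects.
- SAP Section 7.1 says that only one dose was explored in Cohort A and pools the cohorts, which suggests that the dose decision had been made.

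A reader might infer that the definition materially raises the chance of a wrong go decision. The documents do not support a figure for that. They give no 6-week discontinuation rate for the combination. Any calculation would have to treat the rule as mechanical and toxicity stops as separate from named DLTs, although some stops would follow a qualifying delay or reduction. The 14.3% discontinuation rate in Protocol Section 1.4.3 is a monotherapy figure not limited to 6 weeks, so it cannot stand in for the missing rate.

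**Conclusion.** The concern holds as a defect of definition and of consistency between the protocol and the SAP. Read literally, the protocol replaces the most severe drug-related toxicities instead of counting them. The SAP corrects this for discontinuation but not for death. The DLT-evaluable count that the rule uses is not shown in the planned table.

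The effect is conditional. It is zero if no drug-related stop or death occurred in the window, and none is documented. If one occurred and the counted number was 1, the result reads 1/6 (upper limit 42.2%) where it should read 2/6 (58.5%), or 2/7 (51.7%) with the replacement retained. The consequence would be no expansion as the next step. It need not mean closure, because the protocol allows Cohort A to be repeated.

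Three stronger conclusions are not supported:

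- The 42% limit is not wrong. It is correct for DLTs as defined, and the question is what the definition leaves out.
- Nothing shows that expansion was opened improperly.
- Nothing shows that a severe event would have escaped review.

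If Cohort A is complete, what remains is which DLT result is reported and whether at most 1 of 6 still holds under a single definition.

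**What to change.** - Use one DLT definition in Protocol Section 4.5.1 and in both paragraphs of SAP Section 7.6.1. Include drug-related permanent discontinuation of either drug and drug-related death at any time in the 6-week window, so that Cycle 1 stops are clearly covered.
- State that such subjects are DLT-evaluable and are not replaced.
- Keep the table over all treated Cohort A subjects and report beside it the DLT-evaluable count used for the decision.
- Flag replaced subjects, with reasons, in the listings already planned. No new listing is needed.
- State in the report whether at most 1 of 6 holds under the single definition.

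The cost is a few lines of wording, one added count and a flag in existing listings. The downside is that the reported DLT count may be higher. If Cohort A is finished, the SAP and the report are where the change has effect. The protocol wording matters only if Cohort A is reopened or repeated.

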4.3.1 Brentuximab Vedotin

Brentuximab vedotin will be administered every 21 (q 3 weeks) days by IV infusion given over approximately 30 minutes. In the absence of infusion-related reactions, the infusion rate for all subjects should be calculated in order to achieve a 30 minute infusion period. Brentuximab vedotin must not be administered as an IV push or bolus nor mixed with other medications. Brentuximab vedotin will be administered first as a 30 minute infusion followed by a minimum 30 minute rest prior to the nivolumab infusion.

Dosing is based on subject's actual body weight. Doses must be adjusted for subjects who experience a $\geq 10\%$ change in weight from baseline. Other dose adjustments for changes in body weight are permitted per institutional standard. An exception to weight-based dosing is made for subjects weighing greater than 100 kg; doses will be based on 100 kg for these individuals. Rounding is permissible within 5% of the nominal dose.

Refrigeration should be set at 2–8°C for storage of vials and solutions containing brentuximab vedotin. The controlled location must be accessible only to the pharmacist, the investigator, or a designated person. Brentuximab vedotin does not contain preservatives; therefore, opened and reconstituted vials of brentuximab vedotin should be used as soon as possible. If not used immediately, the in-use storage should not be longer than 24 hours. It is recommended that brentuximab vedotin vials and solutions be protected from direct sunlight until the time of use. Reconstituted vials and solutions must not be shaken.

Drug product vials may be labeled as brentuximab vedotin, the United States adopted name (USAN) and the International Nonproprietary Name (INN), or as SGN 35, the compound code; the 2 names can be used interchangeably.

Brentuximab vedotin vials are provided via single-use containers. Any partially used vials or diluted dosing solutions should be discarded using appropriate institutional drug disposal procedures.

Brentuximab vedotin should be reconstituted with 10.5mL of Sterile Water for Injection, United States Pharmacopeia (USP) or equivalent (see Pharmacy Binder for details) for a final concentration of 5mg/mL. The vial should be gently swirled until the contents are completely dissolved. The vial must not be shaken. The reconstituted drug product should be inspected visually for any particulate matter and discoloration.

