7.6.1 Dose Limiting Toxicities

The DLT evaluation period, which consists of the first dose of study drug through the first 6 weeks of treatment, will be conducted in the first 6 treated subjects.

DLTs are defined as any study drug-related toxicity (brentuximab vedotin or nivolumab) that requires either a dose reduction or delay of more than 7 days of either study drug in Cycle 2 or delays the Cycle 3 Day 1 administration of combined treatment by more than 7 days.

Cohort A subjects who have a related AE that require either discontinuation, dose reduction or delay of more than 7 days of either study drug in Cycle 2 or delays the Cycle 3 Day 1 will be categorized as experiencing DLT.

- Number of subjects with dose limiting toxicities will be tabulated (cohort A, all treated subjects)
- A listing will be provided of those subjects containing their reasons for drug discontinuations, delay or reduction and total number of courses received (Cohort A, All treated subjects)

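### The Cycle 3 limb of the DLT definition cannot be observed within the 6-week DLT window, so the expansion review can be held before it is known in the most recently treated subjects

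*Protocol*

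**What the plan says.** Protocol 4.5.1 gives the DLT definition two limbs. A drug-related toxicity is a DLT if it "requires either a dose reduction or delay of more than 7 days of either study drug in Cycle 2", or if it "delays the Cycle 3 Day 1 administration of combined treatment by more than 7 days". The same section fixes the time frame: "The DLT evaluation period consists of the first dose of study drug through the first 6 weeks of treatment". The Synopsis, Protocol 3.1 and SAP 2.1 give the same period, and SAP 7.6.1 repeats both the definition and the window ("The DLT evaluation period, which consists of the first dose of study drug through the first 6 weeks of treatment").

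The review follows from the window: "After 6 DLT-evaluable subjects have been followed through the end of the DLT evaluation period", or as soon as two subjects have a DLT if that is earlier, the study team reviews the data. With "One or none (≤ 1) of the 6 subjects experience a DLT, the expansion cohort will begin" at the tested dose and schedule. Subjects who stop for reasons other than a DLT before the end of the window are replaced; no such provision covers those who stop after it.

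Cycles last 21 days ("Brentuximab vedotin will be administered every 21 (q 3 weeks) days by IV infusion"). The routine dosing tolerance is short: "For all other cycles, treatment is to occur within 3 days of the scheduled dosing date".

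Neither document says that the review waits for Cycle 3 Day 1, or how a subject with a pending Cycle 3 delay is counted.

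**The concern.** The definition looks further ahead than the window in which it is to be assessed. The first limb is safe: Cycle 2 Day 1 is due on Day 22, so a delay of more than 7 days is met by Day 30. The second limb depends on a dose due only after the window has closed.

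This limb matters. The drugs are staggered in Cycle 1 and first given on the same day at Cycle 2 Day 1. Since Cycle 2 dosing falls on its Day 1 only, the Cycle 2 limb mainly picks up toxicity from Cycle 1. Toxicity arising after the first same-day combined dose would qualify mainly through Cycle 3.

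At stake is a decision on six subjects in which one DLT separates expansion from no expansion. A limb that is not yet observable can lower the count but cannot raise it. The evaluability rule has the same gap: a subject who stops for a non-DLT reason after Day 42 but before Cycle 3, for example after the week-6 tumor assessment, stays evaluable although the Cycle 3 limb was never observed.

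**Working it through.** **The plan's own figure.** Protocol 8.1 and SAP 5.1 give a one-sided 80% exact upper limit of 42% for at most 1 DLT in 6. The Clopper-Pearson limit is the 0.80 quantile of Beta(x+1, n−x). For 1/6 it is 42.24%, and for 3/12 it is 41.24% (stated 41.2%). Both reproduce. The 42% describes the DLT rate as defined only if both limbs have been observed in all six subjects.

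**Calendar** (first dose = Day 1, 21-day cycles):

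- Window: 6 × 7 = 42, so it closes on Day 42.
- Cycle 3 Day 1: 1 + 2 × 21 = Day 43.
- Delay of more than 7 days first met: 43 + 8 = Day 51, which is 9 days after the window.
- Cycle 2 started 3 days late: 46 + 8 = Day 54, 12 days after.
- Cycle 2 started 7 days late (not itself a DLT): 50 + 8 = Day 58, 16 days after.
- Counting the 6 weeks from the Day 8 nivolumab dose instead: 8 + 42 − 1 = Day 49, still before Day 51.

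So no reading of the 6 weeks tried here closes the gap.

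**Who is unresolved at the earliest review.** Suppose the review is held on Day 42 of the sixth subject. Any on-schedule subject who started at least 9 days earlier is already at Day 51 or beyond. A subject given Cycle 3 on time is resolved on Day 43. The gap therefore falls on the last subject or last few.

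**Effect on the expansion rule.** The documents give neither the true DLT rate p nor the share g of DLTs that show only through the Cycle 3 limb; both are assumptions. An unresolved subject shows a DLT with probability q = p(1−g).

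- All six resolved: P(≤1) = (1−p)^6 + 6p(1−p)^5. At p = 0.40 this is 0.233.
- One unresolved: P(≤1) = (1−p)^5 + 5p(1−p)^4(1−q). At p = 0.40 this is 0.07776 + 0.2592(1−q).
  - g = 0.25, q = 0.300: 0.07776 + 0.18144 = 0.259.
  - g = 0.33, q = 0.268: 0.07776 + 0.18973 = 0.267.
- Six unresolved: the first formula with q in place of p.
  - q = 0.300: 0.420.
  - q = 0.268: 0.492.

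| Unresolved at review | p = 40%, g = 25% | p = 40%, g = 33% | p = 33%, g = 25% |
|---|---|---|---|
| None | 23.3% | 23.3% | 35.8% |
| One | 25.9% | 26.7% | 38.5% |
| Two | 28.7% | – | 41.4% |
| Six | 42.0% | 49.2% | 54.0% |

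**SAP tabulation.** SAP 7.6.1 states the protocol definition and then gives a categorization sentence for Cohort A that differs from it. That sentence adds discontinuation as a qualifying consequence, and it does not repeat the 7-day threshold for Cycle 3 Day 1. With the 6-week window kept alongside, the reported DLT count is not uniquely defined.

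**The case against.** The strongest reply is that the text sets an earliest point for the review, not a date. The team reviews all available safety data, adverse events are collected continuously, laboratory tests are done within 72 hours before dosing, and the listed recommendations are expressly not exhaustive. Toxicity that threatens Cycle 3 would often be visible around Day 42. The definition can also be read as toxicity arising within 6 weeks and classified later by its effect on Cycle 3. Finally, SAP 7.1 says in the past tense that only one dose was explored in Cohort A, so the decision may already have been made.

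Most of this stands as a limit on size. It does not remove the conflict. The onset reading is not written anywhere, and even under it the count is not final on Day 42. A team that follows the text exactly may decide before the limb is known.

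Three stronger readings should be set aside:

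- A reader might infer that a subject with a pending Cycle 3 delay is counted as DLT-free. The documents are silent on this.
- A reader might infer that the DLT rate is biased downward in general. SAP 7.6.1 includes Cycle 3 delays in its tabulation, so only a count taken at an early review could be low for this reason.
- A reader might take 42–49% as the expected effect. Those figures need the limb to be unseen in all six subjects, which staggered entry makes unlikely; the documents do not give the entry pattern.

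**Conclusion.** The conflict is real and follows from the calendar alone: a 6-week window cannot contain a delay that is first met on Day 51. The consequence is conditional. The expansion review can, but need not, come before the Cycle 3 limb is observable in the most recently treated subjects, and the resulting error runs in one direction, towards expansion.

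Its likely size is modest. At an assumed true DLT rate of 40%, with 25–33% of DLTs showing only through Cycle 3, one unresolved subject adds about 3 percentage points to the chance of expanding. The effect becomes large only as the number of unresolved subjects grows. Nothing in the documents shows that the decision actually taken was affected. Because the passages contradict each other on a go/no-go rule and alignment is cheap, the correction should be made.

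**What to change.** Reconcile four elements wherever they appear (Protocol Synopsis, 1.1.13, 3.1 and 4.5.1; SAP 2.1 and 7.6.1): the evaluation window, the DLT definition, the evaluability and replacement rule, and the review trigger. The test is that every limb of the definition can be observed in all six subjects before the go/no-go count and the SAP tabulation are final. The text should also say how these subjects are counted:

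- a subject with a pending Cycle 3 delay;
- a subject whose Cycle 2 started late;
- a subject who stops for a non-DLT reason between Day 42 and Cycle 3.

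Which element is changed is for the sponsor and investigators to decide; no clinical rule is proposed here.

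In SAP 7.6.1, also reconcile the categorization sentence with the definition above it, on discontinuation and on the threshold for Cycle 3 Day 1.

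The cost is wording, plus up to about 9 days before the Cohort A count is final (51 − 42), or 16 if Cycle 2 started 7 days late (58 − 42). If Cohort A is already complete, no time is lost and the change applies to the reported DLT tabulation.
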